Also accepted as the term expiratory flow acceleration (EFA). It is obtained by the energetic contraction of the expiratory muscles (mainly the abdominal ones). During the maneuver, the intrathoracic pressure of the oral discharge increases simultaneously, which produces a lower mouth discharge that that of coughing, that allows the tearing off of the secretions from the bronchial wall due to the apparition mechanism of the SPP (same pressure point). This situation responds to the function of viscosity, elasticity, mucus thickness, the level of adhesion to the bronchial wall and the flexibility of the bronchial wall.^{*36}

Control Group

The control group (CG) will be subject to PD plus muscle belly compressions of the upper limbs for 10 sessions, one session a day from Monday to Friday, with a duration de 10 to 15 minutes per patient. Both groups will receive the usual treatment for pneumonia prescribed by their treating doctor.

Variables and measuring instruments.

Measurements will be performed before, and 15, 30 and 150 minutes after the maneuvers. Clinical severity will be measured using the Wang score (a modification of the Silverman score) *(Table 3)*, which consists of 4 items:

- 1. Respiratory rate.
- 2. Wheezing.
- 3. Retraction.
- 4. General condition.

Every item has an ordinal measurement level of 0 to 3 points (possible values: 0,1,2,3), excluding general condition (with a value of 0 or 3 only).

With a maximum summation of 12 points and a minimum of 0 points. The higher the score, the higher the clinical severity.

Complementary measurements:

- 1. Heart rate.
- 2. SaO₂.
- 3. Lung occupancy in the x-ray that was taken when the diagnosis was made.

The results from the pediatric Wang score (a modification of the Silverman score) will be compared in and between the groups at the following moments: 1.Before intervention (baseline state), 2.immediately after intervention, 3.15 minutes after intervention and 4.30 minutes after that.

The following tool (anex 2) has been designed to measure the variables. The

resources needed for research development are:

- 1. Medical history.
- 2. Vital signs monitors.
- 3. Stethoscope.
- 4. Pulse oximeter.
- 5. Disposable latex gloves.
- 6. Mechanical aspiration

RESEARCH VARIABLES

Independent variables

- 1. Pediatric respiratory physiotherapy.
- 2. Postural drainage plus muscle belly compressions to the upper limbs.

Dependent variables

- 1. Clinical severity.

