- 2. Days of hospital stay from the beginning of the pneumonia.

Confounding variables

- 1. Baseline disease.
- 2. Age.
- 3. Nutritional state.

Descriptive variables

- 1. Sex.
- 2. Reasons for check-in.
- 3. Heart rate.
- 4. Oxygen saturation (SaO2).
- 5. Lung occupancy.
- 6. Wang score.

Variables	Туре	Instrument	Range
Clinical severity.*	Ordinal.	Wang score.	0-12 pts.
Heart rate.*	Discrete quantitative.	Pulse oximeter. ChoiceMMed MD300C5.	30bpm to 325bpm.
SaO ₂ .*	Discrete quantitative.	Pulse oximeter . ChoiceMMed MD300C5.	0% to 100%.
Lung occupancy.**	Nominal.	Simple X-ray of the thorax.	Identification of the percentage occupied by secretions and infiltrates, detect complications (atelectasis, effusion ,etc).
Days of hospital stay from the beginning of the pneumonia.**	Discrete quantitative.	Clinical file.	0-180 days.
Age.***	Discrete quantitative.	Clinical file.	1 to 6 years 364 days old.
Sex.***	Nominal	Clinical file.	Masculine/femenine.
Baseline disease.	Nominal.	Clinical file.	Yes/No Specify.
Reason for check-in.***	Nominal	Clinical file.	Specify.
Complications of pneumonia from the momento of inclusion.***	Nominal.	Clinical file.	None/ Effusion/ Necrosis or pulmonary abscess/ Other (specify)

*Measurements must be performed before intervention, immediately after, and 15, 30 and 150 minutes after. **Measurements will be performed before

initiating treatment sessions and after they conclude. *** Measurements will be developed previously to the randomized group assignation.

GENERAL DESCRIPTION OF THE STUDY

Assessment prior to the study

- 1. All patients diagnosed with pneumonia who comply with the selection criteria will be invited to participate in the study, in case of accepting, those older than 8 years old will verbally agree and will be given forms of informed consent to sign.
- 2. Data obtained will be documented in a previously established data collection format (Anex 2).
- 3. If there is no contraindication for the procedure, then the maneuver will be assigned.

Initiation and evaluation of the assigned maneuver

- 1. The researcher will perform the maneuver according to group assignation.
- 2. Subsequently a collaborator, previously blinded to the maneuver and standardized for the Wang score (a modification of the Silverman score), will evaluate the Wang score 15, 30 and 150 minutes after its application.

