- 3. Another collaborator will do a follow-up on the patients in order to register their hospital stay time posterior to the diagnosis of pneumonia.
- 4. The assigned maneuver will be performed once a day on the patient.

End of study

The study will end once the patient checks out of the hospital.

Quality control

The assessment of the efficiency will be performed by 2 collaborators blinded to the maneuver. One collaborator will assess the Wang score (a modification of the Silverman score), heart rate and SaO_2 and the other collaborator will register the days of HS.

DATA ANALYSIS PLAN

Descriptive statistic: There will be an assessment of the central tendency values, relative dispersion and disposition to evaluate the descriptive variables at the start and at the end of the studyin both groups, as well as the dependent variables after the intervention.

Inferential statistic:

- 1. The comparison in score of the descriptive variables in and between the groups will be performed using a Mann-Whitney U test.
- 2. A 95% confidence Interval is estimated.

The Wang score rates will be assessed in the measurements made before and immediately after the intervention, and 13, 30 and 150 minutes after.

To describe the measurement differences and to reject or not the hypothesis, a Mann-Whitney U test will be used.

LIMITATIONS OF THE STUDY

Due to the maneuver condition, the subject cannot be blinded, and only the researchers will be single-blinded, which confers a type of bias to the study.

TIMELINE

The timeline of activities is presented as a FORMAT ATTACHED to this document.

ETHICAL CONSIDERATIONS

The 2016 guide for the evaluation of ethical considerations of our institution is presented as a FORMAT ATTACHED to this document.

Beneficence/Nonmaleficence

This is a MAXIMUM TO MINIMAL RISK study for participants, and it could cause reflux, vomit or irritability of the patient's emotional state (with all that implies). Potential benefit to the patient by improving their clinical severity and reducing the days of hospital stay. Potential Benefit to society by reducing the days of hospital stay, which in turn will reduce the cost of treatment for children with pneumonia.

Autonomy and respect

It will be clearly expressed to the patient or person responsible for them, every procedure they will become subject to, until their understanding is secured.

A Form of Informed Consent will be required (Anex 3).

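### The plan applies Mann-Whitney to every descriptive variable within and between groups, but reason for check-in has no order and lung occupancy has no settled scale or timing (minor)

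*Combined protocol and SAP*

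**What the plan says.** **Test.** Under Inferential statistic, the Data Analysis Plan states: "The comparison in score of the descriptive variables in and between the groups will be performed using a Mann-Whitney U test". The same test is used to decide the hypotheses. No test for categorical data appears anywhere in the document.

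**Variables.** The Research Variables section lists six descriptive variables: sex, reason for check-in, heart rate, oxygen saturation, lung occupancy and Wang score. The variables table types three of them as nominal:

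- sex, with the two levels "Masculine/femenine";
- "Reason for check-in", an open field to be specified, with no categories given;
- lung occupancy, whose range entry reads "Identification of the percentage occupied by secretions and infiltrates, detect complications".

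**Timing of lung occupancy.** Under Variables and measuring instruments, the complementary measurements include "Lung occupancy in the x-ray that was taken when the diagnosis was made". In the variables table, lung occupancy carries the double-asterisk footnote, which asks for measurement before "initiating treatment sessions and after they conclude". The descriptive part of the Data Analysis Plan summarises the descriptive variables in both groups at the start and at the end of the study.

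**The concern.** Mann-Whitney ranks values, so it needs an order. Reason for check-in has none. Whoever numbers the categories sets the ranks, and with three or more categories the ranks set the p-value. Lung occupancy has the same problem if it is analysed as the nominal variable that the table declares. As a percentage it would be ordered, but the table puts a percentage and an unordered list of complications in one field, so the analyst cannot tell what is to be ranked.

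The timing adds a second difficulty. If lung occupancy comes only from the diagnostic film, there is no end value and no start-to-end comparison can be made. If the footnote governs, a later value is needed, and the plan does not say where it comes from.

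Third, the sentence covers comparisons within groups as well as between them. Before and after values from the same child are paired, and Mann-Whitney assumes independent samples. It is therefore the wrong test within a group even for ordered variables.

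At stake are the descriptive comparison of the arms, the only imaging measure in the trial, and any within-group p-values that are reported.

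**Working it through.** No stated figure in the plan attaches to this point. The category counts and correlations below are assumed for illustration. The group size of 40 comes from Sample size calculation.

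**1. Unordered variable, three categories A, B, C.** Assumed counts: intervention 20/5/15, control 10/20/10. Totals are 30, 25 and 25, with N = 80.

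- Chi-square, with expected counts 15, 12.5 and 12.5 per arm: 2×5²/15 + 2×7.5²/12.5 + 2×2.5²/12.5 = 3.33 + 9.00 + 1.00 = 13.33 on 2 df, p = 0.0013. Category order plays no part.
- Mann-Whitney: U counts the pairs in which the intervention child has the higher code, plus half the ties. Its null mean is 40×40/2 = 800. Its tie-corrected variance is (40×40/12)×[81 − Σ(t³−t)/(80×79)], with Σ(t³−t) = 26,970 + 15,600 + 15,600 = 58,170. This gives 133.33×(81 − 9.204) = 9,573, SD 97.84, for every numbering. Then z = (|U − 800| − 0.5)/97.84.

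| Order of codes | U | z | two-sided p |
|---|---|---|---|
| A, B, C | 20×5 + 5×20 + 15×35 = 725 | 0.76 | 0.446 |
| B, A, C | 5×10 + 20×25 + 15×35 = 1,075 | 2.81 | 0.005 |
| A, C, B | 20×5 + 15×15 + 5×30 = 475 | 3.32 | 0.0009 |

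The other three numberings are reversals of these and give the same p-values.

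With four assumed categories the effect runs both ways (no continuity correction):

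- 20/4/12/4 against 8/16/4/12: Mann-Whitney p from 0.00003 to 0.52 over all 24 numberings; chi-square p = 0.00014.
- 10/10/10/10 against 15/5/5/15: Mann-Whitney p from 0.046 to 1.00; chi-square p = 0.149.

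**2. Sex, two levels.** Assumed 26/40 against 16/40. Pearson chi-square = 80×(26×24 − 14×16)²/(40×40×42×38) = 5.01, p = 0.0252. The tie-corrected Mann-Whitney without continuity correction equals chi-square × (N−1)/N = 5.01×79/80 = 4.95, p = 0.0261. Reversing the codes changes nothing.

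**3. Lung occupancy.** As a percentage it has an order, so a between-group Mann-Whitney is valid. As a nominal list it falls under step 1. For the start-and-end summary:

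| Source of timing | Start value | End value |
|---|---|---|
| Complementary measurements list | diagnostic film | none |
| Double-asterisk footnote | before sessions | after sessions, source not stated |

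**4. Within-group use.** Simulated pairs with no true change (n = 40, bivariate normal, 4,000 runs, nominal 5%):

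| Assumed correlation | Mann-Whitney type I error | Signed-rank type I error |
|---|---|---|
| 0.5 | 0.7% | 4.8% |
| 0.8 | 0.03% | 4.8% |

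Ignoring the pairing makes the test far too conservative when repeat values are positively correlated.

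**The case against.** The strongest reply is that little depends on these comparisons. Both hypotheses concern the Wang score and days of stay, which are ordered. Sex and reason for check-in are recorded before group assignment, so under proper randomisation any difference is chance. No adjustment, exclusion or decision in the documents rests on these p-values. All of that stands, and it limits the point to a minor one. The assumed counts also show only that numbering can decide the result; they do not show how large the effect would be in this trial.

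The quoted sentence might also be read as covering only scored variables. But it names the descriptive variables as a class. If it were limited in that way, the nominal variables would have no test at all, so the gap remains.

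A reader might go further and infer three things that the documents do not support:

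- **That all three nominal comparisons are invalid.** For two-level sex the test is chi-square in all but name, so it is unconventional and not wrong. For occupancy as a percentage, the between-group ranking is sound.
- **That the footnote orders a further chest film for every child.** It also governs days of hospital stay, for which a value before treatment makes little sense, so it may have been applied loosely. It does not mention a new film, and films from routine care could supply some later values.
- **That different sites would follow different sections.** Recruitment is from one hospital.

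**Conclusion.** The point holds in a limited form and is minor.

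- For reason for check-in, and for lung occupancy if it is analysed as the nominal variable declared, the planned p-value is arbitrary. This follows from the test itself once there are three or more unordered categories; only its size in step 1 rests on assumed counts.
- Lung occupancy has contradictory entries for scale and timing, and on one reading it has no end value for the planned start-and-end summary.
- Within-group Mann-Whitney does not suit paired values, whatever the variable. The size of the loss depends on the correlation between repeat values, which the documents do not give.

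The between-group tests of the Wang score and hospital stay are unaffected, and so is the sample size of 40 per group. Nothing here supports a claim that the trial's main conclusions would be wrong. The data collection form (Anex 2) was not available and may settle how lung occupancy is recorded.

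**What to change.** 1. **Data Analysis Plan.** Limit between-group Mann-Whitney to ordered or numeric variables. Group reason for check-in into categories, and use chi-square or Fisher's exact test for it and for the other nominal variables (for sex this is a matter of convention). For within-group comparisons of ordered or numeric variables, name a paired test such as the Wilcoxon signed-rank.
2. **Variables table.** Record lung occupancy as a numeric percent and put radiographic complications in a separate nominal field. State how that field differs from the existing entry for complications of pneumonia, which comes from the clinical file and is timed before group assignment.
3. **Timing.** Reconcile the complementary measurements list with the double-asterisk footnote. If only the diagnostic film is used, label lung occupancy a baseline descriptor and drop it from the start-to-end comparison.

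The cost is wording in three places, one added field on the data form, and a short category list for reason for check-in. The sample size does not change. If the single-film timing is kept, the trial makes no end-of-study imaging comparison.

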The OBJECTIVE of this research protocol is to evaluate the effectiveness of RPP compared to postural drainage plus compression to the muscle belly of the upper limbs, as an adjuvant treatment for children with pneumonia. It is expected that the clinical severity decreases by 1.5 in the Wang score (a modification of the Silverman score), with a standard deviation of 2.6 points and a decrease of two days in the hospital stay with a α 0.05 in a one-tail test, a P of 80% and a 95.5% confidence interval.

METHODOLOGY, the protocol design corresponds to a single-blind trial. The population will consist of children aged from 0 to 8 years old diagnosed with pneumonia with a development time less than 7 days. The participants who comply with the selection criteria will be grouped in blocks of two using a randomization software (www.radomization.com).

The sample calculation corresponds to 40 participants per group. The intervention group will be exposed to techniques such as prolonged slow expiration, controlled expiratory flow exercises, tracheal pumping and tracheal reflex. The control group will be subject to postural drainage plus compressions to the muscle belly of the upper limbs. Both groups will go through 10 sessions: One daily session from Monday to Friday with a duration of 10 to 15 minutes each.

The Wang score (a modification of the Silverman score) will be used to measure the clinical severity and a pulse oximeter ChoiceMMed MD300C5 for SpO_2 and heart rate readings, the medical records will be consulted during the hospital stay.

DATA ANALYSIS PLAN, to prove whether there are or not statistical differences in and between both groups a Mann-Whitney U test will be used. The weightings from the Wang score (a modification of the Silverman score) will be considered before and immediately after the intervention maneuvers, and after 15, 30 and 120 minutes after said maneuvers have been performed.

BACKGROUND

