To evaluate the prolonged effects (15, 30 and 150 minutes after intervention) of RPP on clinical severity (Wang score (a modification of the Silverman score)) in comparison to PD plus muscle belly compressions to the upper limbs for the treatment of a child with in-hospital pneumonia.

To evaluate the effect of RPP compared to PD plus muscle belly compressions to the upper limbs on the number of days of HS of children with pneumonia.

HYPOTHESIS

1. Children with pneumonia who receive RPP Will have a decrease of 1.5 points, with a standard deviation of 2.6 In the Wang score (a modification of the Silverman score), 30 minutes after it being performed.

2. Children with pneumonia will have a decrease in HS of two days, compared to those treated with PD plus muscle belly compressions to the upper limbs.

METHODOLOGY AND RESEARCH DESIGN

DESIGN

Single-blind randomized clinical trial

Population

1. Study universe: Hospitalized children with pneumonia at the infectiology service.

2. Study population: Children from 0 to 8 years old with a diagnostic of pneumonia (under WHO's criteria) with a development time less than 7 days.

3. Sample: With the support of the epidemiology department, a daily list of all new cases of pneumonia will be provided. Patients then will be included once the diagnostic established by the pneumonia infectiology service is obtained.

Sample size calculation

The calculation for a sample size for an error of α 0.05 in a one-tail test and a power of 80% is based on the values described by Postiaux^{*37} in the difference between the groups 30 minutes after the intervention, during 10 sessions. The difference in the Wang score (a modification of the Silverman score) measurements between the two groups was of 1.5 points with a standard deviation of 2.6 points.

 $\label{eq:states} \begin{array}{l} \Delta \texttt{= 1.5} \\ \texttt{S= 2.6} \\ \texttt{n = 2S}^2(\texttt{Z}_{\alpha/2} + \texttt{Z}_\beta)/\Delta^2 \end{array}$

The participants' sample size will be of 40 per group, to obtain statistical differences in the decrease of the Wang score (a modification of the Silverman score) entre between both groups with a α 0.05 in a one-tail test and a power of 80%, considering a decrease of 36% and a standard deviation of 13%.

Randomization

- 1. A sequence of aleatory numbers in blocks of 2 will be generated in each of the study groups using the software randomization.com, done by a person foreign to the research.

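### Mann-Whitney, the only test named, is also applied to paired before/after Wang scores, and no session or per-child summary is named for the 30-minute value that decides hypothesis 1

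*Combined protocol and SAP*

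**What the plan says.** **Test.** The Summary states: "to prove whether there are or not statistical differences in and between both groups a Mann-Whitney U test will be used". The Data Analysis Plan repeats this: "The comparison in score of the descriptive variables in and between the groups will be performed using a Mann-Whitney U test". The Wang score appears in the list of descriptive variables as well as being the instrument for the dependent variable, so that sentence covers it. The section on variables and measuring instruments says that Wang results "will be compared in and between the groups at the following moments", and the listed moments run from the pre-maneuver baseline to the later readings. The hypothesis itself is decided by the sentence "To describe the measurement differences and to reject or not the hypothesis, a Mann-Whitney U test will be used". No paired or repeated-measures method appears anywhere.

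**Deciding value.** Hypothesis 1 reads "Children with pneumonia who receive RPP Will have a decrease of 1.5 points", at 30 minutes after the maneuver, and names no session and no comparator. Hypothesis 2 does name one: "Children with pneumonia will have a decrease in HS of two days, compared to those treated with PD". The sample-size section takes its figures from a cited study, "in the difference between the groups 30 minutes after the intervention, during 10 sessions", and then says that 40 per group are needed "to obtain statistical differences in the decrease of the Wang score" between the groups. Ten sessions are planned for each child, one per weekday. The footnote to the variables table lists readings before, immediately after, and 15, 30 and 150 minutes after the maneuver.

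**The concern.** There are two separate problems.

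First, Mann-Whitney assumes two independent samples. Before and after scores in one arm are two readings on the same children. If they are positively correlated, the test uses too large a variance for the difference. It then rejects too rarely under the null and can miss a real fall.

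Second, a child with 10 sessions can have up to ten 30-minute readings. That the score is read at every session is an inference from the variables footnote and the daily maneuver; the data form in Annex 2 is not in the text. The test needs one value per child, and the plan does not say whether that is the first session, the last, or a summary. It also does not fully settle whether the value is the score at 30 minutes or its change from the pre-session score. If this stays open until the data are seen, two analysts who both follow the text could report different results for hypothesis 1.

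**Working it through.** **Inputs.** From the sample-size section: difference 1.5, SD 2.6, one-sided α 0.05, power 80%, 40 per group. Assumed: within-child correlation ρ = 0.3, 0.5, 0.7, and a 1-point fall for the within-group example. The documents give neither.

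**1. The plan's own figure.** n = 2 × 2.6² × (1.645 + 0.842)² / 1.5² = 37.2, so 38 per group. This is consistent with the stated 40. (The formula as it appears in the text has an unsquared Z sum and α/2; the stated 40 fits the squared, one-sided form.) Power at 40: 1.5 / (2.6 × √(2/40)) = 2.580; 2.580 − 1.645 = 0.935, which gives 82.5%. Simulation with Mann-Whitney gives 80%. Both assume one value per child.

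**2. Mann-Whitney on paired scores, 40 children.** The test acts as if the mean difference had variance 2σ²/n; the true variance is 2σ²(1 − ρ)/n. Approximate null rejection is therefore P(Z > 1.645/√(1 − ρ)).

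For a 1-point fall the standardised shift is 1 / (2.6 × √(2/40)) = 1.720. Multiplied by √0.955 for rank efficiency, this is 1.681. Approximate power is Φ((1.681 − 1.645)/√(1 − ρ)) for Mann-Whitney and Φ(1.681/√(1 − ρ) − 1.645) for signed-rank.

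| | ρ = 0.3 | ρ = 0.5 | ρ = 0.7 |
|---|---|---|---|
| Type I, Mann-Whitney, approximation | 2.5% | 1.0% | 0.1% |
| Type I, Mann-Whitney, simulation | 2.8% | 1.2% | 0.2% |
| Type I, signed-rank, simulation | 5.4% | 4.9% | 4.8% |
| Power, Mann-Whitney, approximation | 52% | 52% | 53% |
| Power, Mann-Whitney, simulation | 52% | 51% | 52% |
| Power, signed-rank, approximation | 64% | 77% | 92% |
| Power, signed-rank, simulation | 64% | 75% | 91% |

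The simulations used 10,000 replicates. A separate run gave type I error of 2.0/1.2/0.4% and power of 51/53/53% against 63/75/91%. For a 1.5-point fall the gap is smaller: 84/87/93% against 91/97/99.7%.

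**3. Illustration of an open definition.** Take 2.6 as the SD of a single score and test both the raw 30-minute score and the change at one session. The two statistics correlate at √((1 − ρ)/2) = 0.59/0.50/0.39. If the better result is picked afterwards, type I error is 0.05 + 0.05 − P(both significant) = 8.5/8.8/9.1%. Simulation gives 8.3/9.2/9.0%, and the figure cannot exceed 10%. This covers the raw-or-change choice only, not the choice of session.

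**4. What the choice does to power at 40 per arm** (2.6 as single-score SD, true difference 1.5):
- Change score: SD = 2.6 × √(2(1 − ρ)) = 3.08/2.60/2.01. Power is 70/83/95% by formula and 68/80/94% by Mann-Whitney simulation. At ρ = 0.3, 80% power needs 2 × 3.08² × 6.18 / 1.5² = 52.01 (with the unrounded SD), so 53 per arm.
- Session-1 score with a rank test adjusted for the pre-session score (Quade), simulated: 83/88/96%, with null rejection of 4.9-5.2%.

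**The case against.** The strongest reply is that the trial is plainly a comparison of arms. The objectives, research questions and sample size all name the control treatment, and between arms Mann-Whitney is a sound choice for an ordinal score. The within-group error is conservative, so it cannot create a false claim. The wording also leans towards change: the Summary, hypothesis 1 and the sample-size section all speak of a decrease, and the phrase that suggests a raw score describes the cited study. All of that stands. It limits the size of the point but does not remove it. The within-group comparison is stated in three places and has the wrong test, the moment-by-moment comparison keeps a raw reading possible, and nothing names a session or summary.

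A reader might go further and infer any of the following. The documents do not support them.
- That hypothesis 1 is itself a within-group test. It names no comparator, but everything around it is between groups.
- That sessions will be pooled as independent, or success claimed at any session. No section proposes either.
- That discharge biases the comparison. The study ends at discharge and a shorter stay is hypothesised, but the documents give no expected stay for these children, and no bias is shown for change scores. The 72-hour stay is an inclusion criterion, not a count of sessions ahead.

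**Conclusion.** The point holds in two parts of different weight.

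The paired use of Mann-Whitney is wrong as written. Over the assumed correlations its type I error is about 3% to 0.2% instead of 5%, and its power for an assumed 1-point fall is about 51-53% against 63-91%. Because the error is conservative and the main comparison is between arms, this is a should-fix.

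The missing definition of the 30-minute value is the more important wording change, because it decides hypothesis 1. Its full effect cannot be sized from the documents. The 8-10% type I error is an illustration that requires picking between raw and change after the fact.

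It does not follow that the trial is too small or its between-arm test invalid. With one value per child and 2.6 as that value's SD, 40 per arm gives 80-82.5% power.

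**What to change.** 1. Use the Wilcoxon signed-rank test for within-group before/after comparisons. Keep Mann-Whitney for comparisons between arms.
2. Before unblinding, declare one 30-minute value per child for hypothesis 1 and name the control group as comparator. Two reasonable choices are (a) the session-1 score at 30 minutes, compared between arms with a rank test adjusted for the pre-session score (Quade), or (b) a per-child mean over the sessions received, reported with the number of sessions received by arm.
3. Label all other sessions and times as secondary.
4. Reconcile the plan for 10 sessions with the statement that the study ends at discharge.

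**Cost.** Items 1 to 3 are wording only and need no new data. Choice (a) does not measure cumulative effect and departs from the 10-session basis of the planning figures, so 1.5 and 2.6 are only assumed to apply to session 1. An unadjusted change score is the weaker option if 2.6 is a single-score SD and correlation is low: about 68-70% power at 0.3, where 53 per arm would be needed for 80%. The adjusted test avoids that loss, with 83% power at the same correlation. Choice (b) stays closer to the planning basis but averages over a number of sessions that may differ between children.

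### No baseline adjustment is planned for the 30-minute Wang comparison, and the plan does not say whether the Mann-Whitney test takes the raw score or the change

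*Combined protocol and SAP*

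**What the plan says.** **The baseline score is collected.** The footnote to the variables table (Research variables) states: "Measurements must be performed before intervention, immediately after, and 15, 30 and 150 minutes after". The Wang score is among the variables it covers. Variables and measuring instruments lists "1.Before intervention (baseline state") as one of the moments at which the groups are compared. It does not name that score as an adjustment variable.

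**One test is named.** The Data analysis plan says: "To describe the measurement differences and to reject or not the hypothesis, a Mann-Whitney U test will be used". The Summary names the same test. No ANCOVA, ordinal regression or stratified rank test appears. The listed confounders are baseline disease, age and nutritional state, and none is adjusted for. Baseline disease is a yes/no entry from the clinical file, not the starting Wang score.

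**The effect is worded in two ways.** In Sample size calculation it lies "in the difference between the groups 30 minutes after the intervention, during 10 sessions", and the Wang difference "between the two groups was of 1.5 points with a standard deviation of 2.6 points". Under Hypothesis, treated children "Will have a decrease of 1.5 points, with a standard deviation of 2.6". The first fits a comparison of 30-minute scores and the second a change within each child. The SD of 2.6 is attached to both.

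**Design.** There are 40 children per group and 10 sessions per child. Randomisation is in blocks of 2, with no stratification by Wang score stated.

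**The concern.** The same 0-12 score, taken on the same child shortly before the manoeuvre, can be expected to predict the score 30 minutes after it. A two-sample Mann-Whitney test has no place for a covariate. If it is run on raw 30-minute scores, that information is unused, and any chance difference in starting severity passes partly into the answer on hypothesis 1. If it is run on changes, the baseline is used, but with a fixed weight of one instead of the weight the data support. A chance difference is then over-corrected. In both cases precision is given up although the measurement is already made. Leaving the test input open also means it could be chosen after the data are seen.

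**Working it through.** **Inputs from the plan.** Difference 1.5, SD 2.6, one-sided α 0.05, power 80%, 40 per group (Sample size calculation). **Assumed:** correlation ρ between the pre-manoeuvre and 30-minute scores, taken as 0.3 to 0.8, and equal SDs at the two times. The documents give neither.

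**Reproducing the plan's figure.** n = 2S²(z₀.₉₅ + z₀.₈₀)²/Δ² = 2 × 6.76 × (1.645 + 0.842)²/2.25 = 37.15, so 38 per group, close to the stated 40. Allowing for the Mann-Whitney efficiency of 0.955 with normal data, 37.15/0.955 = 38.9, so 39. The formula as printed, with α/2 and the sum of z-values not squared, gives 16.8. The squared one-sided form is therefore the one used here.

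**Variance factors, relative to the raw 30-minute score.** Raw: 1. Change: 2(1 − ρ). ANCOVA: 1 − ρ².

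*Reading A: 2.6 is the SD of the 30-minute score.* Multiply 37.15 by the factor.

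*Reading B: 2.6 is the SD of the change.* Divide each factor by 2(1 − ρ). Raw becomes 1/[2(1 − ρ)], change becomes 1, and ANCOVA becomes (1 + ρ)/2.

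Children per group for 80% power (normal approximation):

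| ρ | A: raw | A: change | A: ANCOVA | B: raw | B: change | B: ANCOVA |
|---|---|---|---|---|---|---|
| 0.3 | 38 | 53 | 34 | 27 | 38 | 25 |
| 0.5 | 38 | 38 | 28 | 38 | 38 | 28 |
| 0.7 | 38 | 23 | 19 | 62 | 38 | 32 |
| 0.8 | 38 | 15 | 14 | 93 | 38 | 34 |

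Example at ρ = 0.5, reading A: 37.15 × (1 − 0.25) = 27.9, so 28. ANCOVA needs the fewest children in every row under both readings.

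**Power at 40 per group.** Reading A: 82.5% unadjusted on normal theory (81.0% for Mann-Whitney), against 85.5%, 90.9% and 97.5% for ANCOVA at ρ 0.3, 0.5 and 0.7. Reading B: 82.5% for change, against 94.0%, 90.9% and 87.6% for ANCOVA.

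**Simulation, reading A.** Whole-number scores clipped to 0-12, control mean 6.5, SD 2.6, 40 per arm, 4,000 runs per setting:

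| ρ | Mann-Whitney, raw | Mann-Whitney, change | ANCOVA |
|---|---|---|---|
| 0.3 | 79% | 67% | 83% |
| 0.5 | 81% | 79% | 90% |
| 0.7 | 80% | 94% | 96% |
| 0.8 | 80% | 99% | 99% |

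Type I error lay between 4.2% and 5.4% for all three. In a separate simulation (mean 6, 3,000 runs), rank ANCOVA had power 81.9%, 88.2% and 94.5% at ρ 0.3, 0.5 and 0.7, against 79.5%, 81.3% and 79.6% for Mann-Whitney on the raw score.

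**Chance imbalance.** If the baseline SD is also 2.6, the baseline difference between arms has SE 2.6 × √(2/40) = 0.58. A difference of at least 0.5 point then has probability 39%, and of at least 1 point 9%. Given a 1-point imbalance, the raw difference is expected to move by ρ (0.3 to 0.7 for ρ from 0.3 to 0.7). The change difference moves by ρ − 1 (−0.7 to −0.3), in the opposite direction. The target is 1.5.

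**The case against.** A reader might infer that the plan ignores the baseline score. The documents do not establish that. Hypothesis 1 is worded as a decrease, the sample size is set for a difference in the decrease, and the Data analysis plan speaks of measurement differences. All of these fit a test on changes, which does use the baseline. The moment-by-moment listing in Variables and measuring instruments points the other way. What stands is that the input is undefined and no adjustment is planned.

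A reader might also infer that the planned test is biased or invalid. It is not. Under randomisation chance imbalance does not inflate type I error, and simulated power on the raw score is about the planned 80%. The issue is efficiency, and the estimate given the imbalance that actually occurs.

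The size of the gain is open to challenge, and that challenge stands. The correlation is undocumented. Scores taken so close together may correlate highly, and a change-score test then loses little under reading A (94% against 96% at ρ 0.7). Under reading B the gain over change scores shrinks as ρ rises. At ρ 0.3 under reading A, rank ANCOVA gains only 81.9 − 79.5 = 2.4 percentage points, and part of linear ANCOVA's advantage comes from leaving ranks. The simulations also do not reproduce the general-condition item, which can only be 0 or 3.

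Finally, a rank test is a reasonable choice for a score that the plan classes as ordinal. That argues for an ordinal adjusted method, not against adjustment.

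**Conclusion.** The point holds as an efficiency and definition matter. The pre-manoeuvre score is mandatory, the only between-arm test is unadjusted, and its input is not specified. Baseline adjustment needs fewer children than the raw or the change comparison at every correlation examined, whichever quantity the SD of 2.6 describes. So the recommendation does not depend on settling that ambiguity, although the size of the gain does. Across ρ 0.3 to 0.7 the ANCOVA requirement is 34 down to 19 per group against 38 for the raw score (reading A), or 25 up to 32 against 38 for the change (reading B). At the unfavourable ends the saving is 4 and 6 children per group.

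These figures assume equal SDs at the two times and an outcome from the same session as the baseline. They need not carry over to a later session or to an average over sessions.

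**What to change.** In the Data analysis plan, replace the between-arm test of hypothesis 1 with wording such as:

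> Hypothesis 1 will be tested by comparing the Wang score 30 minutes after the manoeuvre in session [state which, for example the first] between arms, with the Wang score taken before the manoeuvre in the first session as covariate. The model is [proportional odds / rank ANCOVA / linear ANCOVA]. The unadjusted Mann-Whitney U test on the same 30-minute score is a sensitivity analysis.

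- **Model.** Proportional odds or rank ANCOVA keeps the ordinal treatment. Linear ANCOVA gives an adjusted difference in Wang points with the 95% confidence interval that the plan promises. Choose one in advance.
- **Session.** Name the session that supplies the outcome, and confirm that the 1.5-point difference, taken from data over 10 sessions, is meant to apply to it.
- **Covariate.** Do not adjust for pre-session scores from session 2 onward. They follow treatment, and adjusting for them could remove a carried-over effect.
- **SD.** State whether 2.6 refers to the 30-minute score or to the change.

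The cost is wording only: no new measurement or visit. The sample size does not change, since the largest ANCOVA requirement in the table is 34 per group against 40 planned.
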